#### **Statistical Analysis Plan**

[name] HUM00148853 We will transform skewed outcome variables as needed, run descriptive statistics, apply transformations to assure normality, and assess potential covariates to include. While maximum effort will be made to retain all subjects and minimize the amount of missing data, we anticipate there will be some data lost-to-follow-up and incomplete measures. Thus as is our practice we will address missing data by applying advanced statistical techniques, such as multiple imputation using PROC MI in SAS and IVEWARE SAS macro. Co-I [name] has extensive experience managing datasets with missing data using both Likelihood and Bayesian methods. Both methods are valid when the missing data mechanism is missing at random, which is less restrictive than data missing completely at random. In addition, as needed we will implement sensitivity analysis to assess the robustness of the results under different missing-data mechanisms including missing data that are potentially missing not at random. Co-I [name] has developed and used Bayesian models for sensitivity analysis for different outcomes using these methods. We outline the analytic plan below.

Youth will be randomly assigned to receive intervention or control using a random number assignment protocol we used in the UH2 phase. To test whether the interventions were effective in changing self-regulation targets (Aim 1), medical regimen adherence and T1D health outcomes (Aim 2), and diabetes relevant family processes (on an exploratory basis), we will use an intent-to-treat analysis (all analyses will use an alpha value of p<.05). Baseline comparability of the groups will be assessed for multiple variables using t-tests for continuous variables (e.g., home chaos) and  $\chi^2$  tests for categorical variables (e.g., regimen type). We will use generalized linear (for continuous adherence and health outcomes) and logistic regression (for dichotomous adherent/nonadherent outcomes) to compare changes in SR, adherence and health outcomes across the two groups (treatment vs. control;  $\alpha = 0.05$ ). We anticipate that some children will have only partial adherence to the intervention (i.e. attend a subset of sessions), thus we will conduct a dose-response analysis where dose corresponds to number of sessions, controlling for covariates that relate to number of sessions attended and outcome of interest. Sex will be examined as a biological variable as some differences have been identified in SR-adherence associations. **Power.** In UH3 we will test the feasibility of assaying SR in a new sample and detecting change in SR targets and medication adherence. We anticipate medium effect sizes of 0.6 with the bundled interventions, so our proposed sample size of 94 (47 per group) should result in sufficient statistical Power of 82% to detect such effects using a two-sided Type I error alpha of 0.05. In addition, controlling for baseline variables that relate to outcome would reduce the residual variance and further increase the statistical Power.

**UH3 Study Timeline.** Table 9 outlines the timeline for UH3 activities. We include 3 months of "start-up" to refine assays and interventions (which are largely the same as in the UH2 phase), obtain IRB approval, and train staff. We will enroll 2 new participants per week to reach our recruitment goals (n=94), which is feasible.

The rhythm of data collection in prior studies is similar to that proposed here, and we are thus confident in the feasibility of the project. Co-I [name]'s successful recruitment in the UM Diabetes clinics she runs

| Table 9. Study Timeline                | Sep-
Nov | Dec-
Feb | Mar-
May | Jun-
Aug | Sep-
Nov | Dec-
Feb | Mar-
May | Jun-
Aug |
|--|-------------|-------------|-------------|-------------|-------------|-------------|-------------|-------------|
| Finalize Study Protocols, Train, IRB   |             |             |             |             |             |             |             |             |
| Participant Recruitment, Randomization |             |             |             |             |             |             |             |             |
| 8 week Intervention Period             |             |             |             |             |             |             |             |             |
| Follow-up Assessments                  |             |             |             |             |             |             |             |             |
| Data Analysis and Dissemination        |             |             |             |             |             |             |             |             |
| SOBC and Study Team Meetings           |             |             |             |             |             |             |             |             |

and the large population of youth with T1D (638 youth per year who met study criteria) from which to recruit will help to ensure success. We had no delays in meeting UH2 milestones, even though we had a limited participant pool as we only included children from an existing cohort. In the UH3, we will recruit new participants so we do not anticipate difficulties. As well, the Clinical and Translational Science Award at UM supports Behavioral Clinical Trial Support Units (CTSUs) that provide pre- and post-award support to investigators running behavioral clinical trials (e.g., grants administration specialists; science coordinator). We will coordinate with our Children's and Behavior, Function and Pain CTSU to ensure that we meet IRB, NIH clinical trial, Clinicaltrials.gov, and other regulatory requirements and deadlines for all UH3 study activities.

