## Approach

**Conceptual Model.** The model to be tested using an RCT design in the UH3 phase is presented in Figure 2. We will assess the self-regulation targets of EF, ER, and FO and the proximal validation target of medical regimen adherence

Page **3** of **13** AIMST1D protocol 2021-01-13 using multiple methods (see Tables 6 and 7). Diabetes related health outcomes include HbA1c level and quality of life.

**Participants.** 94 youth between 13.0 and 17.99 years of age will be invited to participate. Inclusion criteria are: 1) youth must have been diagnosed with T1D for at least 6 months; 2) reside with a parent; 3) have HbA1c≥7.0 4) regular access to WiFi; and 5) feel comfortable speaking English enough to complete study activities. Exclusion criteria include: 1) non-fluency in English in parent or youth; and 2) psychiatric or cognitive conditions that would impede ability to participate.

**Recruitment.** There are two recruitment streams for this project. The first and primary source will be patients from UM. The second source of recruitment will be non-Michigan Medicine patients with T1D living in Michigan and northeast Ohio (e.g. Toledo).

The UM Diabetes clinic serves 1300 children with diabetes, primarily T1D. Co-I [name] runs these clinics and has successfully used the below strategies to recruit youth with T1D for multiple studies. The clinic participates in a hospital-wide registry of patients with diabetes and the T1D Exchange. The University of Michigan is one of the leading sites in the T1D Exchange Registry; Co-I [name]'s team enrolled 1009 participants this way (nearly 500 participants were < 18 years old at enrollment). Participants will be recruited from the UM Pediatrics Diabetes Clinic Research Registry and the T1D Exchange T1D Registry.

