Targeted recruitment outreach of all eligible potential participants will be conducted through phone calls, mailings, and emails as well as in-person outreach for UM patients at routine endocrinology appointments and in-person recruitment at fairs, camps and/or community events for any eligible youth with T1D. Electronic advertisements will also be posted on UMHealthResearch.org and clinic website umpedsdiabetes.com. The study team will inform the staff and providers within Pediatric Endocrinology of the study and its requirements and request referrals. Paper advertisements will be distributed in Pediatric Endocrinology clinic rooms at C.S. Mott Children's Hospital and e-newsletter. The team has extensive experience utilizing hospital electronic medical records to screen participants for eligibility.

In addition, the team will utilize listservs and other points of contact (e.g. Facebook groups) of T1D-focused groups in Southeast Michigan. For example, after gaining permission from colleagues at the local chapter of the Juvenile Diabetes Research Foundation (JDRF), the approved study email, flyer, text, and/or umhealthresearch.org link could be sent to members of their listserv or posted to their Facebook group. Project clinicians will also work with outside endocrinologists to have them share the study with their patients. If interested, patients will initiate contact with the study team since the investigators will not have access to other clinic's patient names, addresses or phone numbers. Current families enrolled in the study will also be able to share the study with their T1D network or community via word-of-mouth or by sharing approved recruitment materials; anyone interested would then initiate contact with the study team.

Interested families will complete eligibility screening through an intake call or in person, based on their preferred method. During the intake, informed consent/assent, study activities and random assignment will be detailed. Participants will be randomly assigned to intervention group at enrollment using a random number generator. We will employ a block randomization scheme stratified for youth sex and age (+/- 1 year), to ensure equal allocation to control and intervention groups.

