**Self-regulation.** SR will be assessed using the multi-method assays developed in our UH2 study. Adolescents in the UH3 phase will complete SOBC Network-developed measures that are hypothesized to change as a result of our intervention but that we were not able to use in the UH2 due to the younger age of our sample (e.g., CFC; 5-trial Delay Discounting). All assays were shown to be psychometrically reliable in our own and/or other SOBC Network work, or with adolescents in prior research. EF will be assessed using objective tasks and parent-reports to evaluate working memory (Backward Digit Span; BRIEF); inhibitory control (Go-no-go task; BRIEF); organization/planning (BRIEF). Parents will also complete a digit span and Go-no-go task to assess EF. ER will be assessed using youth self-report and parent-report to evaluate affect dysregulation (SIDES) and perceived stress (NIH PSS) and youth self-report of anxiety (GAD-7) and positive and negative affect (PANAS). FO will be assessed using youth self-report and objective tasks to evaluate self-efficacy (NIH Self-Efficacy), consideration of future consequences of actions (CFC); and delay discounting (5-trial task). We also seek to identify potential mechanisms of association between parent SR capacity and youth T1D outcomes, including diabetes-relevant family processes that have been identified as important in shaping health outcomes for youth with T1D (Table 8).

| Table 6   | Specific Construct   | Measure Details                                | Who / Data Source                               |
|---|--|--|---|
| Intake  |  |  |   |
|   | Regimen (Parent and Child), Parent
Depression, Family Chaos, Family
Composition and Income, Demographics | 29 min   | Parent for all;
Child self-report on Regimen |
| Executive Function  |  |  |   |
| Forward & Backwards
Digit span   | Working memory   | 7 min (online)                                 | Parent and child complete task                  |
| Go No Go task   | Inhibitory control   | 7 min (online)                                 | Parent and child each complete task             |
| Behavior Rating
Inventory of Executive
Function – A                     | EF broad   | 15 min (75 items)                              | Parent self-report                              |

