*Parent Involvement in Diabetes Management* will be measured using the Diabetes Family Responsibility Questionnaire, a 17-item scale that describes diabetes-specific and general health situations or tasks that youth with diabetes commonly engage in. Parents report who, if anyone, in their family takes responsibility for these situations and tasks, including whether the parent and youth share responsibility.

**Covariates.** As in the UH2 phase, demographics and covariates will be assessed in order to include in analyses as needed. These include family income, composition, and medical history; parent depression symptoms (Center for Epidemiologic Studies Depression Scale), youth anxiety, and household stress (CHAOS Scale).

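### The main comparison of changes does not commit to adjusting for the pre-test value of the outcome, or for sex and age, the stratification factors

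*Combined protocol and SAP*

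**What the plan says.** The sentence that defines the main analysis (Statistical Analysis Plan) plans generalized linear models for continuous outcomes and logistic regression for adherent/nonadherent status, "to compare changes in SR, adherence and health outcomes across the two groups". Treatment versus control is the only term it names.

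Other relevant text:

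- **Covariates, in the SAP:** the analysts will "assess potential covariates to include". None is fixed.
- **Covariates section:** "demographics and covariates will be assessed in order to include in analyses as needed". The list continues: "These include family income, composition, and medical history; parent depression symptoms", followed by youth anxiety and household stress. Youth anxiety is also an emotion-regulation measure (Self-regulation section: "youth self-report of anxiety (GAD-7"). Otherwise the list holds no pre-test outcome, and sex and age can enter only as demographics.
- **Randomisation (Recruitment):** a "block randomization scheme stratified for youth sex and age (+/- 1 year").
- **Sex and age in the analysis:** the SAP says sex will be examined as a biological variable, without making it a term in the main model. Age has no stated role.
- **Where adjustment is mentioned:** the dose-response analysis explicitly controls for covariates. The Power paragraph says that control for prognostic baseline variables would cut residual variance and add power. It names no variable and makes no commitment.
- **Data available:** the post-test visit largely repeats the pre-test visit (Procedures). Adherence is recorded at both, in dichotomous and continuous form (Medical Regimen Adherence).

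**The concern.** If the sentence is carried out as written, with arm only, each continuous outcome is compared as a raw change score. That uses the pre-test value only by subtraction, in effect fixing its coefficient at 1. Estimating the coefficient (ANCOVA) never has larger asymptotic variance and usually has smaller. The Power paragraph recognises this benefit, but the analysis sentence does not secure it.

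There are three further consequences:

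- The SAP expects loss to follow-up, and the 82% allows for none, so the unused precision has a purpose.
- Covariates included as needed leave the model open to choice after the data are seen, across many self-regulation, adherence and health outcomes.
- For dichotomous adherence, a logistic comparison of changes is undefined until the plan says how pre-test status enters.

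Leaving out the stratification factors makes the test at most slightly conservative.

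**Working it through.** **Inputs from the documents (Power paragraph):** 47 per group, standardised effect 0.6, two-sided alpha 0.05, stated power 82%.

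**Assumed, because the documents do not give them:** the within-arm pre-post correlation r (0.3 to 0.8); k = pre-test SD divided by post-test SD; whether 0.6 is in SDs of change or of the post-test value; and the share of variance explained by sex and age.

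**1. The stated figure.** Two-sample t-test, noncentrality 0.6 × √(47/2) = 2.91, 92 degrees of freedom: power 82.07%. The 82% reproduces, with no covariate and no dropout.

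**2. Variance ratio.** Taking the post-test variance as 1, the change score has variance 1 + k² − 2rk and ANCOVA has residual variance 1 − r². Their ratio is

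(1 + k² − 2rk)/(1 − r²) = 1 + (k − r)²/(1 − r²),

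which is never below 1. With equal SDs (k = 1) it is 2/(1 + r).

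**3. Equal SDs, 0.6 in change-SD units.** The ANCOVA effect is 0.6 × √(2/(1 + r)), with 91 degrees of freedom.

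| r | Variance ratio | Change score | ANCOVA | ANCOVA n per arm for 82.07% |
|---|---|---|---|---|
| 0.3 | 1.54 | 82.1% | 94.6% | 31 |
| 0.5 | 1.33 | 82.1% | 91.4% | 36 |
| 0.7 | 1.18 | 82.1% | 87.7% | 41 |
| 0.8 | 1.11 | 82.1% | 85.8% | 43 |

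**4. Equal SDs, 0.6 in post-test-SD units.** The change-score effect is 0.6/√(2(1 − r)); the ANCOVA effect is 0.6/√(1 − r²).

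| r | Change score | ANCOVA |
|---|---|---|
| 0.3 | 68.2% | 85.5% |
| 0.5 | 82.1% | 91.4% |
| 0.7 | 96.0% | 98.1% |
| 0.8 | 99.5% | 99.8% |

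A simulation of 20,000 replicates per cell agreed with the tables in steps 3 and 4 to within about 0.7 point.

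**5. Unequal SDs, change-SD units, sex and age also in the model (89 degrees of freedom).**

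| r | k = 0.8: ratio, power | k = 1.25: ratio, power |
|---|---|---|
| 0.3 | 1.27, 90.1% | 1.99, 98.2% |
| 0.5 | 1.12, 86.1% | 1.75, 96.8% |
| 0.7 | 1.02, 82.8% | 1.59, 95.3% |
| 0.8 | 1.00, 82.0% | 1.56, 94.9% |

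Against 82.1%, the gain runs from none to about 16 points.

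**6. Loss to follow-up.** The documents give no rate. If 42 per arm were analysed (about 10% loss, assumed), arm-only power is 77.6%. ANCOVA, under the conditions of step 3, gives 92.1%, 88.0%, 83.8% and 81.7% at r = 0.3, 0.5, 0.7 and 0.8.

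**7. Omitting sex and age.** If they explain a share R² of the variance of the analysed outcome and are balanced by design, true alpha is about 2(1 − Φ(1.96/√(1 − R²))). This gives 0.048, 0.044 and 0.039 at R² = 2%, 5% and 10%. For change scores it is nearer 0.05 if the effects of sex and age are stable over time.

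**8. Degrees of freedom.** These are 92 with arm only, 91 with the pre-test value, 89 with sex and age in years, 86 with five one-year age bands, and 82 with all ten sex-by-age cells. Five bands follow from the age range ("94 youth between 13.0 and 17.99 years of age will be invited to participate"). Going from 91 to 82 lowers the ANCOVA powers in step 3 to 94.6%, 91.3%, 87.7% and 85.8%, a cost below 0.1 point.

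**9. Dichotomous adherence.** Suppose half are adherent at pre-test, the pre-test odds ratio is 8, 50% of controls are adherent at post-test, and the conditional treatment odds ratio is 2.5 (all assumed). Then 67.3% of the intervention arm are adherent, and the unadjusted odds ratio is (0.673/0.327)/(0.50/0.50), about 2.1. The two odds ratios describe the same effect on different scales, so the report must say which is given.

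**The case against.** The strongest reply is that nothing here is wrong. The arm-only comparison is valid, the plan permits covariates, its authors recognise the benefit of baseline control, and if they adjust for the pre-test value the loss is zero. All of that stands. But permission is not commitment, and the sentence as written describes the less efficient analysis.

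Second, the gain rests on inputs outside the documents. That also stands, and no single figure should be quoted. The gain is nil at k = 0.8 and r = 0.8, and about 2 points or less in post-test-SD units at r = 0.7 or above.

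Third, sex and age add little. This is fair: most of the gain comes from the pre-test value. The SAP also gives sex some analytic role, though not an adjustment role. The case for including both is mainly that the analysis should match the randomisation.

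Fourth, the costs are slightly larger than degrees of freedom suggest. Simulated blocked randomisation in ten cells with non-prognostic strata put the cost at 0.2 to 0.6 point. Allowing for chance baseline imbalance raises 31 per arm to 32. Both are negligible.

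Fifth, the logistic model might be sparse, with at most 47 youths in the rarer category even at 50% adherence. Simulation under the assumptions of step 9, with pre-test status, sex and age bands, showed no fitting failures, alpha near 0.05, and about 49 to 50% power against 41% for arm only. That is reassuring for those assumptions; lower or higher adherence or heavy dropout could still produce sparse cells.

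**Conclusion.** The point holds as an improvement that should be made, not as an error. The plan's main comparison names arm alone and fixes neither the pre-test value nor the two stratification factors. For continuous outcomes, ANCOVA is asymptotically at least as precise as the arm-only change score whatever r and k are. Under the equal-SD, change-SD reading the gain is about 4 to 13 points of power over r = 0.8 to 0.3. Across the wider range examined in those units it is 0 to about 16 points. Under the post-test-SD reading it is under 1 to about 17 points. These figures rest on assumed r, k and SD unit, and compare with only one of the analyses the text permits. Regressing change on arm plus pre-test value gives the same treatment estimate as regressing the post-test value, so the question about change is kept. The benefit from sex and age is small and depends on how prognostic they are.

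**What to change.** Replace the analysis sentence with wording such as:

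> Each continuous outcome measured at both visits will be analysed by regressing the post-test value (equivalently, the change) on arm, the pre-test value on the same scale, sex and age (coded as in the randomisation strata), using the planned missing-data methods. Dichotomous adherence at post-test will be modelled by logistic regression on arm, pre-test adherence status, sex and age; the odds ratio is conditional on these covariates and will be reported as such.

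The Recruitment section gives the age strata only as plus or minus one year, so the SAP should also write out the coding actually used. The missing-data methods already planned ("such as multiple imputation using PROC MI in SAS") can stay; any imputation model should contain the same terms as the analysis model. Events taken from chart review are outside this change.

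The cost is SAP wording and the decision to report a conditional odds ratio. No new data, visits or participants are needed. In simulation with sex and age unrelated to outcome and age not balanced by design, adding both cost at most 0.5 point of power.
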